### 7.3.7 BCVA/LLVA

Best corrected visual acuity will be measured by trained and certified personnel at the study sites. The visual acuity (VA) examiner must be masked to each subject's study (treated) eye and treatment arm (study drug vs. Sham) assignment. VA will be measured at the intervals specified in [Table 4](#) and [Table 5](#).

The name and certification number of the vision examiner should be documented in the subject's visual acuity (VA) worksheet (provided by the Sponsor or designee) at each visit. Retroilluminated ETDRS charts are used in this trial. Refraction should be conducted prior to visual acuity testing to obtain best-corrected vision. Best-corrected visual acuity at a starting distance of 4 meters is measured at all office-based study visits using standard charts, lighting, and procedures. The low luminance visual acuity (LLVA) has the same requirements as the best corrected visual acuity; however, the low luminance visual acuity will be measured by placing a 2.0-log-unit neutral density filter over the best correction for that eye and having the participant read the normally illuminated Early Treatment Diabetic Retinopathy Study chart.

A description of the VA assessment is detailed in the Study Procedure Manual or equivalent.

### **7.3.8        Reading Speed**

#### **7.3.8.1        The Minnesota Low-Vision Reading Test (MNRead)**

The Minnesota Low-Vision Reading Test (MNRead) acuity cards are continuous-text reading-acuity cards suitable for measuring the reading acuity and reading speed of normal and low-vision subjects. The Subjects' average reading speed, critical print size, and reading acuity will be calculated using the data transcribed from the scoring sheet to the eCRF and will not be calculated by the interviewers. For additional details see the Study Procedure Manual or equivalent.

#### **7.3.8.2        Radner Reading Cards**

The Radner Reading Cards consist of "sentence optotypes," which are optimized reading test items, standardized by construction and statistical selection. The Radner Reading Cards are suitable for measuring reading speed, reading visual acuity, and critical print size.

The Radner Reading Cards are in the form of a letter-sized booklet with the reading cards and includes clear instructions and evaluation sheets. Eight sentences are printed per page. Each sentence of 14 words is printed on three lines and print sizes vary from 6.3 M to 0.25 M (20/400 to 20/16 at 32 cm). For additional details see the Study Procedure Manual or equivalent.

### **7.3.9        FRI Index**

The FRI Index is a 7-item, interviewer-administered assessment of functional reading independence (see the Study Procedure Manual or equivalent). It has one total index score. The index score is an ordinal scale with higher levels representing higher functional reading independence. The FRI Index has a specified recall period of 7 days. For additional details see the Study Procedure Manual or equivalent.

### **7.3.10        NEI VFQ-25**

The NEI VFQ-25 is a 25-item, interviewer-administered assessment of visual functioning. Near and distance domains will also be included (three additional items for each domain). It is scored on a scale of 0–100, with higher scores indicating better visual function. It has a composite score and 12 domains (general health, general vision, ocular pain, near activities, distance activities, social functioning, mental health, role difficulties, dependency, driving, color vision, and peripheral vision). It does not have a specified recall period. For additional details see the Study Procedure Manual or equivalent.

### **7.3.11        Slit Lamp Biomicroscopy**

Slit lamp biomicroscopy will be performed as determined by the Schedule of Study Procedures ([Table 4](#) and [Table 5](#)).

Grading scales based on the NEI/SUN criteria for the assessment of Anterior Chamber Flare or Cell ([Jabs 2005](#)) and Vitreous Cells and Haze ([Nussenblatt 1985](#)) are provided in [Appendix 1](#).

Slit-lamp exam must be performed before the instillation of any dilating or anesthetic eye drops or fluorescein agent. Subject will remain seated for this exam.

### **7.3.12        Intraocular Pressure**

Goldmann tonometry or Tono-pen tonometer is required at routine study visits for pre- and post-dose intraocular pressure assessments. The method of IOP measurement used for a patient must remain consistent throughout the study. If pathological measurements are obtained with Tono-pen, contact-tonometry should be performed.

#### **7.3.12.1        Post Injection Assessment**

A measurement of intraocular pressure of either the study eye or both eyes (depending on the visit; refer to [Table 4](#) and [Table 5](#)) will be obtained approximately 15 minutes after any IVT injection by qualified unmasked site staff. If there are no safety concerns, the subject will be permitted to leave the clinic. The IOP values recorded in mmHg will be entered into the eCRF. If the IOP post-dose is  $\geq 30$  mmHg, the subject should remain in clinic and be measured again approximately 30 minutes later (45–60 minutes post-injection).

Pressure lowering drops are permitted at Investigator discretion. If there are no safety concerns at that time, and the IOP is  $< 30$  mmHg, the subject will be permitted to leave the clinic. The last post-injection IOP value will be recorded on the appropriate eCRF.

In the case of an acute IOP spike ( $\geq 30$  mmHg from pre-injection IOP as measured at  $\geq 60$  minutes post-injection), which causes pain and loss of vision, a paracentesis may be performed in the anterior chamber, to release some aqueous humor and relieve the pressure. The final pre-intervention IOP recording as well as the post-intervention IOP recorded will be entered into the applicable eCRF page. If applicable, an Adverse Event eCRF page will be completed.

### **7.3.13        Dilated Fundus Exam and Indirect Ophthalmoscopy**

Ophthalmoscopy will be performed as identified in the Schedule of Study Procedures ([Table 4](#) and [Table 5](#)).

After the pupil is dilated, the optic nerve and macular are evaluated at the slit lamp with a 90/78/60 diopter (or similar) lens. This is followed by Indirect Ophthalmoscopy (IO) which examines for vitreous haze (the degree of inflammation) and the peripheral retina, looking for retinal tears after injection among other things. Both the slit lamp and IO are done together to evaluate the posterior segment.

### **7.3.14 Ocular Imaging**

Central reading center will be used to perform an independent analysis of all images. The central reading center will provide sites with the Central Reading Center manual and training materials for specified study ocular images. Before any study images are obtained, site personnel, test images, and systems and software (where applicable) will be verified/validated by the reading center as specified in the Central Reading Center manual. All ocular images results will be obtained by trained site personnel at the study sites and forwarded to the central reading center for independent analysis and/or storage. Note: after randomization, if a subject misses a study visit during which ocular images were scheduled to be taken, the images should be obtained at the next scheduled visit ([Table 4](#) and [Table 5](#))

Ocular images obtained for the purpose of the study should include the following:

- Spectral domain Optical Coherence Tomography (SD-OCT)
- Fundus autofluorescence (FAF)
- Color Fundus Photography (CFP)
- Fluorescein angiography (FA)

Additional details on obtaining these images are included in the Central Reading Center Manual.

#### **7.3.14.1 SD-OCT**

Spectral Domain Optical Coherence Tomography (SD-OCT) will be collected as determined by the Schedule of Study Procedures ([Table 4](#) and [Table 5](#)). SD-OCT will be performed at the study sites by trained personnel who are certified by the central reading center. SD-OCT imaging will be performed for each subject at the intervals specified in [Table 4](#) and [Table 5](#). Once images are collected, they will be forwarded to the central reading center.

#### **7.3.14.2 Fundus Autofluorescence**

Fundus Autofluorescence (FAF) will be performed at the study sites by trained personnel who are certified by the central reading center. FAF imaging will be performed for each subject at the intervals specified in [Table 4](#) and [Table 5](#). Once images are collected, they will be forwarded to the central reading center.

#### **7.3.14.3 Color Fundus Photography (CFP)**

Color Fundus Photography (CFP) will be taken by trained personnel at the study sites. Fundus photography will be performed at the intervals specified in [Table 4](#) and [Table 5](#). Once images are collected, they will be forwarded to the central reading center.

#### **7.3.14.4        Fluorescein Angiography (FA)**

Fluorescein angiography will be performed at the study sites by trained personnel who are certified by the central reading center. The fluorescein angiograms (FAs) will be obtained at the intervals specified in [Table 4](#) and [Table 5](#). Once images are collected, they will be forwarded to the central reading center.

#### **7.3.14.5        Microperimetry**

Mesopic microperimetry of study eye only will be performed at select study sites by trained personnel who are certified by the central reading center. Microperimetry will be performed on subjects who meet eligibility criteria as defined in [Section 5](#).

The microperimetry results of the study eye will be obtained at protocol-specified visits, as specified in [Table 4](#) and [Table 5](#), and will be forwarded to the central reading center for additional review.

### **7.3.15        Management of Choroidal Neovascularization (CNV)**

While subjects with active CNV in their study eyes are excluded from this study, it is possible that CNV develops during the duration of the study.

**Diagnosis:** Subjects suspected of clinical CNV development in the study eye must have the diagnosis confirmed with SD-OCT and FA. CNV confirmation by the Central Reading Center, using both imaging modalities, is required prior to initiation of anti-VEGF treatment. On the study visit where CNV is suspected by the evaluating physician, and the additional imaging is taken and submitted for Central Reading Center review, it is allowable to proceed with the study dosing per the assessment schedule while awaiting Central Reading Center feedback on CNV diagnosis. Once the diagnosis is confirmed the patient can be administered aflibercept (EYLEA®). This may require a separate visit (unscheduled visit). If there is a patient safety concern please reach out to the medical monitor to discuss management.

#### **7.3.15.1        Management of Choroidal Neovascularization (CNV)-Study Eye**

**Treatment (Study Eye):** In this protocol, only aflibercept (EYLEA®) is allowed. Follow routine clinical practice in administering aflibercept per FDA label. Treatment frequency with anti-VEGF should be based on standard of care regimens to maximize long-term visual outcomes and minimize recurrence and subject burden.

**Study Drug (Study Eye):** In subjects who developed CNV in their study eye and have a confirmed diagnosis from the Central Reading center, study drug will continue but it will be administered after anti-VEGF treatment, once the IOP has returned to a normal range (< 30 mmHg), approximately 15–30 minutes after the anti-VEGF injection. At the

physician's discretion, maneuvers such as mild ocular digital massage may be applied to the globe prior to the injection to reduce the risk of complications secondary to increased IOP.

A measurement of intraocular pressure will be obtained approximately 15 minutes after the second IVT injection by qualified unmasked site staff. If there are no safety concerns, the subject will be permitted to leave the clinic. The IOP values recorded in mmHg will be entered into the eCRF. If the IOP post dose is  $\geq 30$  mmHg, the subject should remain in clinic and be measured again approximately 30 minutes later (45–60 minutes postinjection). Pressure lowering drops are permitted at Investigator discretion. If there are no safety concerns at that time, and the IOP is  $< 30$  mmHg, the subject will be permitted to leave the clinic. The last postinjection IOP value will be recorded on the appropriate eCRF.

In the case of an acute IOP spike ( $\geq 30$  mmHg from preinjection IOP as measured at  $\geq 60$  minutes post the second injection), which causes pain and loss of vision, a paracentesis may be performed in the anterior chamber, to release some aqueous humor and relieve the pressure. The final preintervention IOP recording as well as the postintervention IOP recorded will be entered into the applicable eCRF page. If applicable, an Adverse Event eCRF page will be completed.

**Study Subject (Study Eye):** Subjects receiving CNV treatment will continue in the study until end of the study (Week 56). If subjects opt to discontinue study drug, they should still continue with study visits and assessments through Week 56.

#### **7.3.15.2 Management of Choroidal Neovascularization (CNV)-Non-Study Eye**

**Treatment (Non-Study Eye):** In subjects with CNV in the non-study (fellow) eye, follow routine clinical standard of care in diagnosis and treatment. If non-study eye treatment will occur on the same day as a study dosing visit, the study eye should be dosed first. There are no other specific treatment stipulations for non-study eye.

**Study Drug (Non-Study Eye):** In subjects with CNV in the non-study (fellow) eye, study drug will not be stopped.

**Study Subject (Non-Study Eye):** Subject will continue in the study until end of the study.

#### **7.3.16 Clinical Genotyping Sample**

An optional one-time buccal swab will be collected for genetic marker analysis at any time during the study post-randomization (Day 1 to EOS). Collection will only occur if the subject has consented to the optional procedure on the consent form and there are no laws or study center policies in place that prohibit the collection of samples for genetic marker analysis. The genetic marker sample will be used to evaluate the relationships between genetic polymorphisms associated with AMD, baseline disease characteristics, and response to

administration of NGM621. If a subject does not want to participate in this optional sample collection, this does not preclude their participation in the trial.

## **7.4 Safety and Other Assessments**

### **7.4.1 Adverse Events**

#### **7.4.1.1 Definition of Adverse Events**

An adverse event (AE) is defined as any untoward medical occurrence in a subject or clinical investigational subject who has been administered a pharmaceutical product that does not necessarily have a causal relationship with this treatment. A treatment-emergent adverse event (TEAE) is an AE that is reported after a dose of study drug.

AEs are all:

- unfavorable changes in general condition.
- subjective or objective signs/symptoms.
- concomitant diseases or accidents.
- clinically relevant adverse changes in laboratory parameters observed in a participant in the course of a clinical study.

AEs comprise all disturbances of general health status, subjective and objective disease symptoms (including laboratory abnormalities), and accidents observed in the context of a clinical trial, irrespective of a possible causal relationship with the administration of the trial substance. Events occurring in the framework of a clinical trial during drug-free, and post-treatment periods, or under placebo, are also to be designated as AEs.

All AEs, whether volunteered, elicited, or noted on physical examination, will be recorded throughout the study (i.e., from screening until end of study [EOS]).

Subjects will be queried for resolution of ongoing AEs or until any unresolved AEs are judged by the PI to have stabilized or if lost to follow up. Resolution of all AEs will be promptly documented by the clinic in the subject's eCRF.

Any pregnancy diagnosed during the study must be reported immediately to the Investigator and Sponsor, including pregnancy in female partners of male subjects. The pregnancy will be followed to term and/or outcome and this outcome must be reported to the Sponsor.

Pregnancy, in and of itself, is not regarded as an AE or serious adverse event (SAE) unless the birth results in a congenital anomaly/birth defect or there is suspicion that the study treatment may have interfered with the effectiveness of a contraceptive medication or method.

The PI will rate the severity of systemic AEs and ocular AEs using different scales. The PI will rate the severity of systemic AEs using the CTCAE v5 to grade the severity. Each CTCAE v5 term is a Medical Dictionary for Regulatory Activities (MedDRA) Lowest Level Term (LLT). The CTCAE displays Grades 1–5 with unique clinical descriptions of severity for each AE. Not all Grades are appropriate for all AEs. Therefore, some AEs are listed with fewer than five options for Grade selection. Grade 5 (Death) is not appropriate for some AEs and, therefore, is not an option.

The PI will rate the severity of ocular AEs using the definitions below. For each episode, the highest severity grade attained should be reported.

**MILD** = Does not interfere with subject's usual function (awareness of symptoms or signs, but easily tolerated [acceptable]).

**MODERATE** = Interferes to some extent with subject's usual function (enough discomfort to interfere with usual activity [disturbing]).

**SEVERE** = Interferes significantly with subject's usual function (incapacity to work or to do usual activities [unacceptable])

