## 7.2 Study Visit Procedures

### 7.2.1 Screening (Day -28 to Day -3) Visit

The following procedures will be performed at Screening:

- Obtain informed consent
- Inclusion/exclusion criteria assessment
- Demographics
- Ocular and medical history
- Physical Exam
- Measure body weight
- Serum pregnancy test for female subjects of child-bearing potential
- Hematology, Chemistry
- Urinalysis
- Urine drug screen
- Collect adverse events and concomitant medications
- Measure vital signs (including temperature, respiratory rate, and seated blood pressure and pulse)
- BCVA on both eyes
- LLVA on both eyes
- Intraocular pressure on both eyes
- Slit lamp biomicroscopy on both eyes
- Dilated fundus exam and indirect ophthalmoscopy on both eyes
- SD-OCT on both eyes
- Fundus autofluorescence on both eyes

- Fluorescein angiography on both eyes
- Color fundus photography on both eyes
- Microperimetry (at selected sites) on study eye
- Schedule Day 1 visit

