#### **PRE-DOSE**

- Urine pregnancy test for female subjects of child-bearing potential. If pregnancy is suspected, a serum pregnancy test may be conducted
- Adverse events and concomitant medications
- FRI Index
- NEI VFQ-25
- BCVA on both eyes
- Measure reading speed
- Intraocular pressure on both eyes (prior to dilating eyes)
- Slit lamp biomicroscopy on both eyes
- Dilated fundus exam and indirect ophthalmoscopy on both eyes
- Microperimetry (at selected sites) on study eye
- Serum sample for PK
- Serum samples for ADA and NAb
- Serum sample for C3 and CH50
- **CCI** [REDACTED]
- **CCI** [REDACTED]
- Randomize and dose all subjects (Q4W and Q8W), as randomized

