#### **8.4 Safety Analyses**

Adverse events will be coded using the Medical Dictionary for Drug Regulatory Activities (MedDRA). Ocular and systemic treatment emergent adverse events (TEAEs) will be summarized by primary system organ class and preferred term. Actual values and change from baseline values for vital signs, clinical laboratory (hematology and chemistry) tests and other continuous variables (both ocular and non-ocular) will be summarized with descriptive statistics. Concomitant medications, physical examinations, and other categorical (safety) variables (both ocular and non-ocular) will be summarized with frequency and percentage distribution. All safety analyses will be performed using the Safety Analysis Set.

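### A treatment-emergent adverse event is defined by when it is reported, not by its onset or worsening

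*Combined protocol and SAP*

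**What the plan says.** Section 7.4.1.1 gives the only definition of the term: a TEAE "is an AE that is reported after a dose of study drug". It has no onset criterion, no worsening criterion and no end of window.

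The same section has AEs recorded from screening to end of study, and adds: "Events occurring in the framework of a clinical trial during drug-free, and post-treatment periods, or under placebo, are also to be designated as AEs". Section 7.2.1, headed "Screening (Day -28 to Day -3) Visit", includes AE collection. The Day 1 pre-dose list in Section 7.2.2 repeats it ("Adverse events and concomitant medications").

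For ocular AE severity, Section 7.4.1.1 instructs: "For each episode, the highest severity grade attained should be reported". Section 7.4.1.6 says that once a diagnosis is established, earlier reports of its signs and symptoms are nullified and replaced by a single report whose start date is that of the first symptom.

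For analysis, Section 8.4 states: "Ocular and systemic treatment emergent adverse events (TEAEs) will be summarized by primary system organ class and preferred term". The Synopsis says the same, and neither place redefines the term. Section 3.1 names the incidence and severity of ocular and systemic AEs, compared with Sham, as the primary safety endpoints.

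**The concern.** A treatment-emergent flag is meant to separate events that began or got worse under treatment from those already present. A flag based on report date does something else: it sorts events by when the subject or site mentioned them. Because AE recording starts before dosing, the database will hold events on both sides of the first dose, and the flag has to sort them.

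The AE table by system organ class and preferred term is the only AE tabulation the plan describes, so any misclassification feeds directly into the safety comparison. A programmer would either have to apply the sentence literally or substitute an onset rule that is written nowhere. The sentence also sits awkwardly beside the protocol's own causality guidance (Section 7.4.1.4 and Table 7), which looks to the timing of event onset relative to study drug. Causality is judged by onset, whereas treatment emergence is judged by report.

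**Working it through.** No figure in the plan depends on this definition, so there is nothing to recompute. The check is to run typical cases through the sentence as written and compare the result with an onset-or-worsening rule.

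| Case | Relevant text | TEAE as written? | TEAE by onset or worsening? |
|---|---|---|---|
| 1. Begins after the first dose and is reported then | 7.4.1.1 | Yes | Yes |
| 2. Begins before Day 1, is first mentioned at Week 1 and does not worsen | 7.4.1.1; Week 1 AE collection in 7.2.3 | Yes | No |
| 3. Symptoms reported before dosing; diagnosis made after dosing without worsening, and the new report replaces the old with the first symptom's start date | 7.4.1.6 | Yes | No |
| 4. AE reported at screening or at the Day 1 pre-dose query worsens after injection; the site raises the grade on the existing record | 7.4.1.1, highest grade per ocular episode | No | Yes |
| 5. As case 4, but the site enters the worsening as a new AE | 7.4.1.1, unfavorable changes count as AEs | Yes | Yes |
| 6. Condition recorded as ocular or medical history worsens after dosing and is first entered as an AE then | 7.3.2 and 7.4.1.1 | Yes | Yes |

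The two rules differ in cases 2, 3 and 4.

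- **Case 2** follows from the wording alone.
- **Case 3** needs no late reporting. It arises when a site follows Section 7.4.1.6 correctly, which puts the report and the start date on opposite sides of the first dose.
- **Case 4** depends on site practice. Nothing calls for a new record when an existing AE worsens, and one highest grade per ocular episode points toward updating the old record. An update leaves no separate post-dose report for the rule to pick up. Case 5 shows that a site acting differently would have the event counted, so identical clinical courses can be classified differently.

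Two possible rescues within the text were checked.

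- The opening AE definition refers to subjects who have been given a product, which might seem to exclude pre-dose events. The same section nevertheless records AEs from screening.
- Section 8 lets the final SAP prevail over the protocol, but only for discrepancies with that section. The TEAE definition is in Section 7.4.1.1, and the text available here contains no separate SAP definition.

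**The case against.** The strongest case on the other side is that this is a loose sentence with little practical effect. Much of that stands.

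- The Day 1 pre-dose AE query intercepts many events that would otherwise surface only at Week 1.
- Conditions present at entry are collected as history, so their post-dose worsening would be a new AE and would count (case 6).
- Worsening can be seen elsewhere. Section 8.4 also summarizes change from baseline and categorical safety variables, ocular and non-ocular, and Section 7.4.1.8 makes sight-threatening events SAEs with no treatment-emergence condition.
- AE start dates are recorded, so an onset rule could be applied at analysis, and the promised SAP might do so.

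Several stronger readings are tempting, and the documents do not support them.

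- A reader might infer that every post-dose worsening of a reported AE is lost. Case 5 shows that a site may enter it as a new AE. What can be said is that no rule ensures it is captured.
- A reader might infer a bias toward no difference, on the view that drug-induced worsening disappears mainly from the NGM621 arms. No rate of such worsening is given for any arm, so no direction can be claimed.
- A reader might take the pre-dose share of collection time as a cap: 28 days of screening and 56 × 7 = 392 days of follow-up give 28 / (28 + 392) = 6.7%. That is a share of calendar time, not of events, and it bounds nothing. An event that began even before screening and was first mentioned at Week 1 would also count under the literal rule.
- A reader might take the words study drug to mean that Sham subjects can have no TEAEs. Section 8.1 uses the same words to define the mITT set, which must include Sham subjects for the primary comparison.
- A reader might call TEAE incidence the primary safety endpoint. Section 3.1 names AE incidence and severity; TEAEs enter through the planned tabulation.

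None of this makes report date the right criterion.

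**Conclusion.** Wrong as written. The definition sets an explicit rule, and that rule is not one of treatment emergence. It counts some events with pre-dose onset and has no criterion to capture post-dose worsening of an AE already reported before dosing. It should be corrected because the only specified AE tabulation, and through it the primary safety endpoint, rests on it.

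The affected set is probably small, for the reasons conceded above. Its size and any direction of bias cannot be derived, since the documents give no count of pre-dose or worsening events. The over-counting in cases 2 and 3 follows from the text. The gap in case 4 is an inference that assumes sites update an existing record rather than open a new one. The conclusion also assumes that no SAP text outside the material available here already defines TEAEs by onset or worsening.

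**What to change.** Replace the sentence in Section 7.4.1.1 with a definition along these lines, and repeat it in the SAP: a TEAE is an AE with onset, or worsening in severity, on or after the first study treatment (NGM621 or Sham) through Week 56. Naming both treatments also removes the loose use of study drug.

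Classify events by the recorded AE start date, which Section 7.4.1.6 shows is already part of the AE report. This settles cases 2 and 3.

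For case 4, state in Section 7.4.1.1, next to the ocular severity instruction, that post-dose worsening of an AE ongoing at first dose must be recorded so that it can be identified, for example as a new entry with its own start date. Reconcile this with the highest-grade-per-episode rule, which as it stands points the other way.

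The cost is an edit to the definition, a matching line in the SAP and a small change to the AE recording instructions given to sites. Design, sample size and visit schedule are unaffected.
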